7.2.4. Preexisting Medical Conditions

A preexisting medical condition is one that is present at the start of the study. Such conditions should be recorded on the Medical History and Baseline Conditions eCRF.

If a preexisting medical condition increases in frequency or severity, or if the character of the condition worsens during the study, the condition should be recorded as an AE or SAE. When recording such events on the AE eCRF, it is important to convey the concept that the preexisting condition has changed by including applicable descriptors (eg, "more frequent headaches").

7.2.5. Worsening of Sickle Cell Disease

SCD- related AEs that are common complications associated with the study participant's SCD may not be considered related to voxelotor unless judged by the Investigator to have worsened in severity and/or frequency or changed in nature during the study. SCD-related AEs include: SCA with crisis, ACS, pneumonia, priapism and osteonecrosis (Kato, 2018).

7.2.5.1. Vaso-Occlusive Crisis

VOC is defined as a composite of acute painful crisis and/or ACS. In order to allow for an assessment of VOC events while minimizing variability in reporting and assessment, additional data will be collected for SCD-related AEs (eg, acute painful crisis, ACS events).

7.3. Serious Adverse Events, Serious Adverse Drug Reactions, and Requirements for Immediate Reporting

All SAEs, regardless of causal attribution, must be reported by the Investigator/designee or site personnel within 24 hours of SAE awareness on the AE eCRF via the EDC system. In the event that the EDC system is not available, paper SAE report forms will be used to report the SAE and faxed or emailed to the Sponsor or designee. The information reported on paper SAE report form should be entered into the EDC once available.

The Sponsor or designee may request additional source documentation pertaining to the SAE from the investigational site. Follow-up reports must be submitted within 24 hours of awareness and ensure that participant identifier information (eg, name, medical record number) are redacted in the hospital discharge summaries, autopsy reports, and/or death certificates.

Follow-up SAE information must be submitted within 24 hours of awareness as additional information becomes available.

Note: The following guidelines are included to support Study transition to Pfizer Pharmacovigilance processes and systems.

Follow-up by the Investigator continues throughout the active collection period and until the AE or SAE or its sequelae resolve or stabilize at a level acceptable to the Investigator. For participants who are screen failures, the active collection period ends when screen failure status is determined.

If the participant withdraws from the study and also withdraws consent for the collection of future information, the active collection period ends when consent is withdrawn.

If a participant permanently discontinues or temporarily discontinues voxelotor because of an AE or SAE, the AE or SAE must be recorded on the CRF.

Investigators are not obligated to actively seek information on AEs or SAEs after the participant has concluded study participation. However, if the Investigator learns of any SAE, including a death, at any time after a participant has completed the study, and they consider the event to be reasonably related to voxelotor, the Investigator must promptly report the SAE to the Sponsor.

7.3.1. Reporting Suspected Unexpected Serious Adverse Reactions and Urgent Safety Issues

The Sponsor or its designee is responsible for reporting Suspected Unexpected Serious Adverse Reactions (SUSARs) to regulatory agencies, competent authorities, IRBs/ECs, and Investigators as per local laws and regulations. Fatal and life-threatening SUSARs will be submitted no later than 7 calendar days of the Sponsor's or CRO designee first knowledge of the event and followup information submitted within an additional 8 calendar days, or as otherwise required per local laws and regulations. All other SUSARs will be submitted within 15-calendar days of the Sponsor's or CRO designee first knowledge of the event. The Investigator is responsible for notifying the local IRB or local ECs of all SAEs that occur at his or her site as required by local regulations or IRB/EC policies, if this responsibility resides with the site.

Investigators are required to report any urgent safety matters to the Sponsor or its designee within 24 hours of awareness. The Sponsor or its designee will inform regulatory authorities, IRBs/ECs, and Investigators, as applicable of any events (eg, change to the safety profile of voxelotor, major safety findings that may place study participants at risk) that may occur during the clinical trial that do not fall within the definition of a SUSAR but may adversely affect the safety of study participants.

7.4. Reporting Pregnancy

If a participant becomes pregnant while taking study drug, the study treatment will be immediately discontinued, and the pregnancy must be reported to the Sponsor or designated Drug Safety CRO within 24 hours of awareness. The Investigator will discuss the risks and concerns of investigational agent exposure to a developing fetus and counsel the participant and/or pregnant partner (or ensure such counseling is provided).

Reported pregnancy of a participant or a participant's partner while participating in this study will be monitored for the full duration of the pregnancy, and/or followed through a definitive outcome (ie, birth, or spontaneous or elective abortion). Pregnancies in partners of male study participants will similarly be monitored for the full duration of the pregnancy and/or followed through a definitive outcome (ie, birth, or spontaneous or elective abortion).

An uncomplicated pregnancy will not be considered an AE or SAE. Pregnancy complications such as spontaneous abortion/miscarriage and congenital anomalies are considered SAEs and must be reported as described in Section 7.3. Note: an elective abortion is not considered an SAE. Pregnancy and pregnancy outcomes must be reported on a Pregnancy Notification or Pregnancy Outcome Form, respectively, and sent to the Sponsor or designated Drug Safety CRO within 24 hours of the Investigator, designee, or site personnel learning of the pregnancy or pregnancy outcome.

The child born to a female participant or participant's partner exposed to study drug will be followed for 3 months after delivery. The outcome of any pregnancy and the presence or absence of any congenital abnormality will be recorded in the Pregnancy Outcome Form and reported to the Sponsor or designated Drug Safety CRO. Any congenital abnormalities in the offspring will be reported as an SAE and must be reported as described in Section 7.3.

Information regarding pregnancy testing (including definition of females of child-bearing potential) is provided in Section 5.8. Highly effective means of contraception are listed in Section 5.9.

7.5. Reporting Overdose

If a participant takes more than the protocol-defined dose in a day and experiences a drug-related AE, this will be reported as an overdose and a protocol deviation. However, if the participant did not experience any AEs, this will only be reported as a protocol deviation.

The Investigator will discuss the risks and concerns of investigational agent exposure with the participant. Parents, guardians or participants are to be instructed to contact their study site

immediately if an overdose of study drug is suspected. An overdose with AEs must be followed until the adverse effects are resolved or stabilized, or until reasonable attempts to determine resolution of the event are exhausted.

In the event of an overdose, the Investigator or treating physician should:

- 1. Contact the study Medical Monitor within 24 hours.
- Closely monitor the participant for any AEs/SAEs and laboratory abnormalities medically appropriate and follow up until resolution, stabilization, the event is otherwise explained, or the participant is lost to follow-up.
- Document the quantity of the excess dose as well as the duration of the overdose in the eCRF.
- 4. Report to Sponsor Safety only when associated with an SAE.

7.6. Environmental Exposure, Exposure During Pregnancy or Breastfeeding, and Occupational Exposure

Note: This section is included to support Study transition to Pfizer Pharmacovigilance processes and systems.

Environmental exposure occurs when a person not enrolled in the study as a participant receives unplanned direct contact with or exposure to voxelotor. Such exposure may or may not lead to the occurrence of an AE or SAE. Persons at risk for environmental exposure include healthcare providers, family members, and others who may be exposed. An environmental exposure may include exposure during pregnancy (EDP), exposure during breastfeeding (EDB), and occupational exposure.

Any such exposures to voxelotor under study are reportable to the Sponsor or designee within 24 hours of Investigator awareness.

7.6.1. Exposure During Pregnancy

An EDP occurs if:

- A female participant is found to be pregnant while receiving or after discontinuing voxelotor.
- A male participant who is receiving or has discontinued voxelotor inseminates a female partner.
- A female nonparticipant is found to be pregnant while being exposed or having been exposed to voxelotor because of environmental exposure. Below is an example of environmental EDP:
 - A female family member of healthcare provider reports that she is pregnant after having been exposed to voxelotor by all possible routes of exposure, eg, ingestion, inhalation, or skin contact.
 - A male family member or healthcare provider who has been exposed to voxelotor by all possible routes of exposure, eg, ingestion, inhalation, or skin contact, then inseminates his female partner prior to or around the time of conception.

The Investigator must report EDP to the Sponsor or designee within 24 hours of the Investigator's awareness, irrespective of whether an SAE has occurred. The initial information submitted should include the anticipated date of delivery (see below for information related to termination of pregnancy).

- If EDP occurs in a participant/participant's partner, the Investigator must report this
 information to the Sponsor or designee regardless of whether an SAE has occurred.
 Details of the pregnancy will be collected after the start of voxelotor and until at least
 140 days after the last dose.
- If EDP occurs in the setting of environmental exposure, the Investigator must report
 information to the Sponsor or designee. Since the exposure information does not
 pertain to the participant enrolled in the study, the information is not recorded on a
 CRF; however, a copy of the completed report is maintained in the Investigator site
 file.

Follow-up is conducted to obtain general information on the pregnancy and its outcome for all EDP reports with an unknown outcome. The Investigator will follow the pregnancy until completion (or until pregnancy termination) and notify the Sponsor or designee of the outcome as a follow-up to the initial report. In the case of a live birth, the structural integrity of the neonate can be assessed at the time of birth. In the event of a termination, the reason(s) for termination should be specified and, if clinically possible, the structural integrity of the terminated fetus should be assessed by gross visual inspection (unless pre-procedure test findings are conclusive for a congenital anomaly and the findings are reported).

Abnormal pregnancy outcomes are considered SAEs. If the outcome of the pregnancy meets the criteria for an SAE (ie, ectopic pregnancy, spontaneous abortion, intrauterine fetal demise, neonatal death, or congenital anomaly in a live-born baby, a terminated fetus, an intrauterine fetal demise, or a neonatal death), the Investigator should follow the procedures for reporting SAEs. Additional information about pregnancy outcomes that are reported to the Sponsor or designee as SAEs follows:

- Spontaneous abortion including miscarriage and missed abortion should be reported as an SAE;
- Neonatal deaths that occur within 1 month of birth should be reported, without regard to causality, as SAEs. In addition, infant deaths after 1 month should be reported as SAEs when the Investigator assesses the infant death as related or possibly related to exposure to voxelotor.

Additional information regarding the EDP may be requested by the Sponsor. Further follow-up of birth outcomes will be handled on a case-by-case basis (eg, follow-up on preterm infants to identify developmental delays). In the case of paternal exposure, the Investigator will provide the participant with the Parental Partner: Information Sheet and Informed Consent Form to deliver to his partner. The Investigator must document in the source documents that the participant was given the Pregnant Partner Release of Information Form to provide to his partner.

7.6.2. Exposure During Breastfeeding

An EDB occurs if:

- A female participant is found to be breastfeeding while receiving or after discontinuing voxelotor.
- A female nonparticipant is found to be breastfeeding while exposed or having been exposed to voxelotor (ie, environmental exposure). An example of environmental EDB is a female family member or healthcare provider who reports that she is breastfeeding after having been exposed to voxelotor by all possible routes of exposure, eg, ingestion, inhalation, or skin contact.

The Investigator must report EDB to the Sponsor or designee within 24 hours of the Investigator's awareness, irrespective of whether an SAE has occurred. When EDB occurs in the setting of environmental exposure, the exposure information does not pertain to the participant enrolled in the study, so the information is not recorded on a CRF. However, a copy of the completed report is maintained in the Investigator site file.

7.6.3. Occupational Exposure

The Investigator must report any instance of occupational exposure to the Sponsor or designee within 24 hours of the Investigator's awareness regardless of whether there is an associated SAE. Since the information about the occupational exposure does not pertain to a participant enrolled in the study, the information is not recorded on a CRF; however, a copy of the completed report is maintained in the Investigator site file.

7.7. Medication Errors

Note: This section is included to support Study transition to Pfizer Pharmacovigilance processes and systems.

Medication errors may result from the administration or consumption of voxelotor by the wrong participant, or at the wrong time, or at the wrong dosage strength.

Medication errors are recorded and reported as follows:

Table 10: Reporting of Medication Errors

Recorded on the Medication	Recorded on the Adverse	Reported to the Sponsor Within
Page of the CRF	Event Page of the CRF	24 Hours of Awareness
All (regardless of whether associated with an AE)	Any AE or SAE associated with the medication error	Only if associated with an SAE

Abbreviations: AE, adverse event; CRF, case report form; SAE, serious adverse event.

Medication errors include:

- Medication errors involving participant exposure to the study drug
- Potential medication errors or uses outside of what is foreseen in the protocol that do
 or do not involve the study participant
- The administration of an incorrect dosage;

- The administration of expired study drug;
- · The administration of an incorrect study drug;
- The administration of study drug that has undergone temperature excursion from the specified storage range unless it is determined by the Sponsor that the study drug under question is acceptable for use.

Whether or not the medication error is accompanied by an AE, as determined by the Investigator, such medication errors occurring to a study participant are recorded on the medication page of the CRF, and, if applicable, any associated serious and nonserious AE(s) are recorded on the AE page of the CRF.

In the event of a medication dosing error, the Sponsor or designee should be notified within 24 hours.

Medication errors resulting in an AE or SAE should be reported to the Sponsor or designee within 24 hours via eCRF.

7.8. Data and Safety Monitoring Board

See Section 3.1.4 for information regarding the DSMB.

8. DATA ANALYSIS AND STATISTICAL PLANS

8.1. Endpoints

8.1.1. Primary Endpoint

The primary efficacy endpoint is the change from Baseline at 24 weeks in TAMMV arterial cerebral blood flow, as measured by TCD.

8.1.2. Secondary Endpoints

The secondary endpoints are:

- Change from Baseline in TCD flow velocity at Week 48 and Week 96
- Time to conversion to abnormal TCD flow velocity (≥ 200 cm/sec)
- Time to reversion to normal TCD flow velocity (< 170 cm/sec)
- Proportion of participants with TCD flow velocity reduction ≥ 15 cm/sec at Week 24, Week 48, and Week 96
- Change in Hb from Baseline at Week 24, Week 48, and Week 96
- Change in clinical measures of hemolysis (unconjugated bilirubin, % reticulocyte, absolute reticulocyte, and lactate dehydrogenase [LDH]) from Baseline at Week 24, Week 48, and Week 96
- Annualized incidence rate of reported VOCs

8.1.4. Safety Endpoints

The safety endpoints include AEs, clinical laboratory assessments, and vital signs.

8.1.5. Pharmacokinetic Endpoints

The endpoint is whole blood and plasma voxelotor PK as evaluated by PPK analysis using nonlinear mixed effects modeling.

8.2. Sample Size

The sample size is planned to provide sufficient statistical power for the primary efficacy analysis and for a robust safety database. In addition, the number of events required to assess secondary efficacy endpoint, eg, percentage conversion to abnormal TCD category, is also considered.

For the primary endpoint (change from Baseline in TCD flow velocity [cm/sec]), assuming equal allocation across treatment groups and a common variance, an estimate of the number of participants in each of 2 treatment groups used the following assumptions in the power calculation:

- Targeted treatment effect: difference in mean change from Baseline in TCD flow velocity is 15 cm/sec
- Common standard deviation is 24 cm/sec
- A significance level of 5% (2 -sided)

Assuming a 20% drop out rate, a sample size of 112 participants per group provides > 95% power to detect the targeted treatment effect for the following hypothesis test using a Student's t-test:

H ₀ : μ ₁ =μ ₂	versus	H _A : μ1≠μ2,
and but but	· CLOCKO	True her / her?

where μ_1 and μ_2 stand for mean change from Baseline in TCD flow velocity at Week 24 in voxelotor and placebo groups, respectively.

For the secondary efficacy endpoint of time to conversion to abnormal TCD category, assuming 35% of participants in the placebo group have experienced a TCD flow velocity > 200 cm/sec by Week 96, a hazard ratio of 0.5 between voxelotor group and placebo, a fixed follow up time of up to 96 weeks for each participant, and an overall 20% drop out rate, a total of 49 events is expected. This provides approximately 65% power for a log-rank test at a two-sided significance level of 5% and approximately 75% power at a two-sided significance level of 10% (PASS version 11).

8.3. Populations for Analysis

The following populations will be considered in the analysis of data. Assignment or exclusion of participants from the analysis populations will be performed prior to study unblinding.

Intent to Treat (ITT) Population: The ITT population includes all randomized participants. This is the primary analysis population for efficacy, demographics, and baseline characteristics data. Participants will be grouped according to the treatment group to which they are randomized.

Safety Population: All participants who receive at least 1 dose of study treatment will be included in the safety population. This is the primary analysis population for safety and exposure data. Participants will be grouped according to the study treatment they receive.

PK Population: The PK population will consist of all participants who receive active study drug and have at least 1 measured concentration at a scheduled PK time point after the start of dosing. If any participants are found to be noncompliant with respect to dosing or have incomplete data, protocol violations, or clinical events that affect PK, a decision will be made on a case-by-case basis as to their inclusion in the analysis. Participants in this population will be used for all PK summaries.

8.4. Efficacy Analysis

8.4.1. Efficacy Analysis

8.4.1.1. Primary Endpoint

The primary analysis of change in TCD flow velocity from Baseline to Week 24 will be performed using a mixed model for repeated measures (MMRM). Independent variables will include treatment, study visit, treatment by study visit interaction, and randomization stratification factors (ie, HU use, age, Screening TCD flow velocity, and geographic region). Within-subject variability will be modeled using an unstructured covariance matrix.

8.4.1.2. Secondary Endpoints

The secondary endpoints will be analyzed as described below.

Change from Baseline endpoints

Change in TCD flow velocity from Baseline to Week 48 and Week 96 will be analyzed with the same MMRM as described for the primary endpoint (change from Baseline in TCD flow velocity at Week 24). A single model will be fit incorporating data from all timepoints.

Change in Hb and clinical measures of hemolysis (unconjugated bilirubin, % reticulocytes, absolute reticulocyte, and LDH) from Baseline at Week 24, Week 48, and Week 96 will be analyzed with a similar approach.

TCD responder endpoint

The TCD responder endpoint, defined as a TCD flow velocity reduction from Baseline ≥ 15 cm/sec at a given timepoint, eg, Week 24, Week 48, or Week 96, will be analyzed using an exact Cochran-Mantel-Haenszel (CMH) general association test stratified by the randomization stratification factors for the treatment difference between voxelotor and placebo.

A sensitivity analysis will be performed to assess TCD response definition with various TCD cutoff values in addition to the proposed 15 cm/sec.

Time to event endpoints

For time to conversion from conditional to abnormal TCD, the Kaplan-Meier method will be used to estimate the landmark rates and the associated 95% confidence intervals in the voxelotor and placebo groups at Week 24, Week 48, and Week 96. A log-rank test stratified for the randomization stratification factors will be used to test the difference between voxelotor and placebo groups. A Cox proportional hazard model may be used to estimate the hazard ratio, as appropriate.

Time to conversion to abnormal will be calculated as the number of weeks from the date of randomization to the date of TCD assessment when a TCD flow velocity \geq 200 cm/sec is first observed. For participants who withdraw from the study without conversion to abnormal or who reached analysis data cutoff date without TCD flow velocity reaching abnormal range, their time to conversion to abnormal will be censored at the date of last TCD assessment prior to study withdraw or analysis data cutoff date, as applicable.

Time to reversion from conditional to normal TCD will be analyzed using a similar approach.

Annualized incidence rate of VOCs will be calculated for each treatment group (total number of events)/(total subject-years). The associated 95% exact Poisson confidence limits will be reported. Mean cumulative functions for VOC incidences will be presented for each treatment group.

8.4.2. Missing Data Handling

The analysis of change from Baseline in TCD flow velocity using MMRM will primarily be based on all available data. For participants discontinued from study treatment due to conversion to abnormal TCD flow velocity (Section 3.1.1), TCD values post study drug discontinuation will be imputed with last observation carried forward. Sensitivity analysis may be performed with various methods of missing data imputation, eg, multiple imputation, to assess the robustness of the MMRM analysis outcomes.

Participants who discontinue treatment prior to the endpoint visit due to conversion to abnormal TCD or stroke or TIA will be considered non-responders. Participants with a missing TCD flow

velocity value will be assessed for TCD response based on the most recent non-missing TCD flow velocity prior to the endpoint visit.

Detailed considerations of missing data handling are described in the statistical analysis plan (SAP).

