2. INTRODUCTION

The purpose of Study GBT440-032 (C5341021) is to evaluate the effect of voxelotor on reducing the risk of stroke, as measured by transcranial doppler (TCD) flow velocity in subjects 2 to < 15 years of age with sickle cell disease (SCD) who have conditional TCD flow velocity at baseline.

This document describes the statistical methods to be used in the summary and analysis of data from Study GBT440-032. Population pharmacokinetic (PK) analyses will be described in a separate document. Descriptive statistics for **CCI** may be summarized in a separate report. Where this document differs from the study protocol, the methodology described in the SAP is considered the latest and supersedes the corresponding section(s) in the protocol.

As of 1 May 2024, study drug dosing in GBT440-032 was voluntarily paused by the Sponsor due to a safety imbalance. Study visits and other study activities continued in accordance with the protocol. Subsequently, a decision was made by the Sponsor on 25 September 2024 to terminate the study based on the totality of clinical data for Oxybryta (voxelotor) and the last subject last visit occurred subsequently.

[figure not shown]

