6.4.2.3. TCD Responder

A TCD responder is defined as a TCD flow velocity reduction from Baseline ≥ 15 cm/sec, and will be assessed separately at Week 24, Week 48, and Week 96.

- Subjects with a missing TCD flow velocity value at the assessment timepoint will be classified as non-responders.
- Subjects initiating HU postbaseline are to be discontinued from the study. TCD assessments obtained after HU initiation will be excluded from analysis (considered missing).
- RBC transfusions: TCD results within 8 weeks after the transfusion date will be imputed for the analysis of TCD response. Post transfusion results will be imputed by data from the most recent study visit prior to the transfusion (including Baseline) with a non-missing TCD value.

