8.2. Efficacy Analyses

Efficacy analyses will be based on the ITT patient population (Section 7), with subjects grouped according to the treatment assigned at randomization. Data from all randomized subjects, regardless of adherence to study drug or to the protocol will be included in the efficacy analyses. This includes data from subjects who discontinued study drug early but continued with study assessments.

Covariate Adjustment

Unless otherwise noted, analyses of primary and secondary efficacy endpoints will be adjusted (see Section 8.2.1 and Section 8.2.2) for the following randomization stratification variables:

- Baseline HU use (yes; no)
- Age (2 years to \leq 8 years; $>$ 8 years to $<$ 15 years)
- Screening TCD value (170 cm/sec to $<$ 185 cm/sec; 185 cm/sec to $<$ 200 cm/sec)

Note: The randomization stratification variable of geographic region (Africa including MENA; rest of world) as stated in the protocol is not included as a covariate as the vast majority of enrolled subjects are from a single region (Africa including MENA).

For stratification variables, the value recorded in the clinical database (ie, per case report form [baseline HU use and age] or by the central reading center [Screening TCD flow velocity]) will be compared to value captured in the IXRS. If differences are observed, the values from the clinical database will be used in the analysis.

Statistical Tests

All statistical tests will be conducted at a two-sided alpha level of 0.05. Adjustment for multiple comparisons is described in Section 8.2.6.

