8.2.6. Adjustment for Multiple Comparisons

To control the overall significance level (alpha) for the study at a 2-sided 5% level, a fixed sequence hierarchical test procedure will be used to formally evaluate voxelotor treatment effect in comparison to placebo at Weeks 24 and 48.

The primary and key secondary endpoints will be tested in the following order:

1. TCD flow velocity change from Baseline at Week 24 (primary endpoint)
2. TCD flow velocity change from Baseline at Week 48
3. TCD flow velocity response rate at Week 24

Each endpoint will be tested at a 2-sided alpha level of 5%. Testing of endpoints subsequent to a non-significant result will be considered exploratory in nature. Per Section 6.3 (Analysis

090177e1a2bf4d41Approved\Approved On: 31-Jan-2025 17:16 (GMT)

Timing), summaries of Week 96 or time to event efficacy endpoints based on partial data will be considered exploratory.

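### The SAP drops, without explanation, the protocol's rule that stopping treatment for conversion, stroke or TIA is a TCD non-response, leaving a small gap in a formally tested endpoint

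*Protocol*

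**What the plan says.** Protocol section 8.4.2 has two separate rules for TCD response. The event rule is: "Participants who discontinue treatment prior to the endpoint visit due to conversion to abnormal TCD or stroke or TIA will be considered non-responders". The missing-value rule scores anyone who lacks a reading on the latest one obtained before that visit.

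SAP section 6.4.2.3 begins "A TCD responder is defined as a TCD flow velocity reduction from Baseline ≥ 15 cm/sec" and attaches no condition about clinical events. It then gives three data rules:
- Missing value: "Subjects with a missing TCD flow velocity value at the assessment timepoint will be classified as non-responders".
- Hydroxyurea (HU) started after baseline: later TCD values count as missing, so the child is a non-responder.
- Red cell transfusion: a TCD result in the following 8 weeks is replaced by the value from the last visit before the transfusion.

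SAP section 8.2.2.3 repeats the missing-value rule. Neither section mentions treatment stopped for conversion, stroke or TIA.

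Three other SAP statements matter:
- Section 2: where the documents differ, "the methodology described in the SAP is considered the latest and supersedes the corresponding section(s) in the protocol".
- Section 8.2, on the data included in efficacy analyses: "This includes data from subjects who discontinued study drug early but continued with study assessments".
- Section 8.2.6: the third and last item in the fixed testing sequence is "TCD flow velocity response rate at Week 24".

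The SAP's summary of changes for version 2.0 reports the new missing-value rule. It does not mention the loss of the event rule.

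**The concern.** The two protocol rules do different jobs. One says how to fill a gap in the data. The other says that certain clinical failures are not successes. The SAP rewrote the first and left out the second. Because the SAP takes precedence, the second no longer operates.

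A non-response rule triggered only by a missing value does not act when a value exists. After a stroke or TIA, a child may have a TCD in the Week 24 window that is at least 15 cm/sec below baseline. If the child was transfused, a good value from before the event may be put in its place. Either way the child is scored as a responder. In a trial whose purpose is to reduce stroke risk, that is a misclassification in an alpha-controlled endpoint.

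The SAP handles comparable cases more strictly elsewhere. For hemoglobin response (section 8.2.3), HU started before Week 24 or a transfusion within 8 weeks of the assessment is a non-response. For the primary model (section 8.2.1), missing values after conversion are drawn from readings of 200 cm/sec or more. None of the listed sensitivity analyses covers the dropped event rule.

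**Working it through.** **Plan's own figures.** No figure is given for the responder endpoint. The neighbouring ones reproduce. With 112 × 0.8 ≈ 90 per arm, SD 24 and difference 15, t-test power is 98.6% (stated: above 95%). Conversion events are 0.8 × 112 × [0.35 + (1 − 0.65^0.5)] = 89.6 × 0.544 = 48.7 (stated: 49). The planning inputs are therefore used below.

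**Rules side by side**

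| Situation before Week 24 | Protocol 8.4.2 | SAP 6.4.2.3 / 8.2.2.3 |
|---|---|---|
| Stopped for conversion, stroke or TIA; no later TCD | Non-responder | Non-responder (missing) |
| Same; TCD value in window | Non-responder | Scored on that value |
| Same; TCD in window and within 8 weeks after transfusion | Non-responder | Scored on last pre-transfusion value |
| Missing for another reason | Last earlier value | Non-responder |

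The documents differ in rows 2 to 4. The gap described here is rows 2 and 3. In row 4 the SAP is the stricter of the two.

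**Stop days at risk.** Protocol 3.4.2.2 puts End of Study 28 days after the last dose. SAP Table 1 gives Week 24 as Days 141 to 182 and has no separate End of Study window. So 141 − 28 = 113 and 182 − 28 = 154, which is 42 days. With the ±7 days shown for End of Study in Appendix C, the range is 141 − 35 = 106 to 182 − 21 = 161, which is 56 days. This route needs a TCD at End of Study. The TCD row of Appendix B is not readable, so that is an assumption.

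**Strokes in that period, per arm of 112.** Protocol 1.1 gives about 2% per year for conditional velocities. Protocol 1.5 gives 2% to 5% without a time unit, so 5% per year is an assumption. Each stroke is taken to lead to a treatment stop. TIAs are not counted because the documents give no rate.
- 112 × 0.02 × 42/364 = 0.26
- 112 × 0.05 × 42/364 = 0.65

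**Chance that a pre-event value qualifies** (SD 24, effect 15; placebo mean change assumed 0):
- Placebo: Φ(−15/24) = Φ(−0.625) = 0.266
- Voxelotor: Φ((−15 + 15)/24) = Φ(0) = 0.50

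**Expected false responders, equal stroke rates**
- Placebo: 0.26 × 0.266 = 0.07 to 0.65 × 0.266 = 0.17
- Voxelotor: 0.26 × 0.50 = 0.13 to 0.65 × 0.50 = 0.32
- With the 56-day range (multiply by 56/42): about 0.09 to 0.23 and 0.17 to 0.43

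One child is 1/112 = 0.89 percentage points. The upper voxelotor figure for 42 days is 0.32/112 = 0.29 points.

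**Direction.** If stroke were halved on voxelotor, as the plan assumes for conversion (hazard ratio 0.5), the relative contributions would be 0.5 × 0.50 = 0.25 on voxelotor and 1 × 0.266 = 0.27 on placebo. The imbalance disappears.

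**Conversion route.** With exponential times and full follow-up, conversion by Week 24 is 1 − 0.65^(24/96) = 10.2% on placebo and 1 − 0.65^(0.5 × 24/96) = 5.2% on voxelotor. That is 11.4 + 5.9 ≈ 17 of 224 children. To score as a responder, such a child must then fall from 200 or more to 155 (baseline 170), or to just under 185 (baseline just under 200). HU start makes the value missing. A transfusion after conversion normally brings back the abnormal reading. Few of the 17 could qualify.

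**Could one child matter?** Only near the boundary. With assumed counts and an unstratified Fisher test in place of the exact CMH test, 45/112 against 30/112 gives p = 0.047, and 44/112 against 30/112 gives p = 0.064.

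**The case against.** The strongest reply is that the SAP already does most of the work. The protocol's event rule sits under missing data, beside a carry-forward rule, and one of its effects was to stop an early stopper being scored on an old good value. Once carry-forward is replaced by missing equals non-responder, nearly the same children are covered, and other missing values are treated more strictly. SAP section 6.4.2.1 also speaks of missing values after an abnormal TCD, which suggests that such children are expected to have none. Much of this stands: the gap is confined to children with a usable value in the window, and for converters it is nearly empty. It does not close the stroke and TIA route, and the protocol's rule is not limited to children with missing values.

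Two stronger readings are tempting, and the documents support neither.
- A reader might count every stroke in the first 24 weeks: 112 × 0.02 × 24/52 = 1.0 to 112 × 0.05 × 24/52 = 2.6 per arm. But the protocol sends a child who stops to End of Study 28 days after the last dose, so an earlier stop gives a Week 24 value only if assessments continue off drug. SAP 8.2 allows for that, but the documents give no frequency.
- A reader might infer a bias toward voxelotor. That needs equal event rates in both arms and average TCD responses before a stroke. With fewer events on voxelotor the lean vanishes, and the plan itself expects more conversions on placebo.

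It is also fair that only the Week 24 response is formally tested. Week 48, the 30 cm/sec definition and the Week 24/28 average lie outside the sequence.

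**Conclusion.** The omission is real. A protocol rule was lost without a stated reason, and the SAP followed literally can score a child who stopped for stroke or TIA as a Week 24 responder. The expected number is well below one child per arm: about 0.07 to 0.17 on placebo and 0.13 to 0.32 on voxelotor. This rests on a TCD being done at End of Study, a 2% to 5% yearly stroke risk, a stop after each stroke, equal rates in the arms, and pre-event changes that follow the planning assumptions with a placebo mean of 0. Conversion adds little. Each error adds a responder to its own arm, but the net effect on the difference between arms could go either way. Severity is minor: a cheap correction of a clear misclassification, unlikely to change the result.

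**What to change.** Restore the event rule in SAP sections 6.4.2.3 and 8.2.2.3, placed ahead of the missing-value and transfusion rules. Suggested wording: a subject who discontinues study treatment before the assessment timepoint because of conversion to abnormal TCD, stroke or TIA is a non-responder at that and all later timepoints, whatever TCD value is later observed or substituted. Apply it to the 15 and 30 cm/sec definitions, to the Week 24/28 average, and at Weeks 24, 48 and 96.

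SAP section 6.3 says the primary analysis, including the secondary Week 24 endpoints, was already performed. The change should therefore be labelled post hoc, or the protocol-rule result reported as a sensitivity analysis beside the SAP result. Either way, list the affected children by arm with their TCD values. If the omission was deliberate, state the reason.

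No new data are needed. The costs are a possible very slight fall in response rates and the post hoc label.
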